8.2.2.2. Analysis of Secondary Endpoints of Expansion Component

8.2.2.2.1. Overall Survival (OS)

OS will be analyzed and displayed graphically using the Kaplan-Meier method for each expansion cohort separately. The median event time and corresponding two-sided 95% CI will be provided for expansion MDS and AML cohorts separately.

The Kaplan-Meier estimate of survival probabilities at 12, 18, and 24 months and their two-sided 95% CI (using log-log transformation and back-transformation) will be provided for each cohort separately.

The FAS will be used.

8.2.2.2.2. Other Efficacy Measures

Specifically, for AML cohort, the following binary efficacy endpoints (with 95% exact CI) will be summarized in frequency tables, proportion of patients achieving CR, CRh, CRi, CR/CRi, MLFS, PR, SD, CRc, , CRm, and CR+PR.

For MDS cohort, the following binary efficacy endpoints (with 95% exact CI) will be summarized in frequency tables, proportion of patients achieving CR, marrow CR, PR, SD, CR+PR, and Partial or Complete Cytogenetic Response, as well as the proportion of patients ever achieving HI.

The FAS will be used.

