 - **Type of Bone Marrow Sample:** For all patients, a bone marrow aspirate sample is required at every disease evaluation, and will be used for both local clinical staging and centralized biomarker assessments. Bone marrow biopsies are optional unless required for clinical staging (eg, dry tap). Samples taken prior to consent but within the 28-day window may be used for disease evaluation and need not be repeated. Bone marrow samples required for other study assessments (eg, MRD assessment) must be collected after consent is signed. We recommend, but do not require, patients sign an informed consent prior to a diagnostic bone marrow aspiration to avoid an additional procedure to collect bone marrow aspirate for the biomarker assessments required during screening
 - **Timepoints for Bone Marrow Sampling:** Bone marrow assessment must be completed at screening (within 28 days prior to first dose), C7D1 (-3/+14 days) (unless done earlier due to suspected CR), C13D1 and every 12 cycles thereafter (C25D1, C37D1, C49D1, etc), and at any time as per investigators discretion if CR is suspected. No bone marrow assessment is necessary if non-response or progressive disease can be diagnosed from peripheral blood evaluation or radiological/clinical assessment.
17. **Bone Marrow Genetics:** Genetics analysis (local), including karyotyping, will be conducted on all patients using any scheduled or unscheduled bone marrow samples collected during study participation. Genetics to be analyzed are specified in [Appendix 3](#) for MDS patients and [Appendix 16](#) for AML patients. Baseline genetics classification must be completed on a sample collected within 28 days prior to first dose.

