9.3.6. Other Efficacy Measures

Additional efficacy measure of interest for the safety LIC and expansion MDS cohort include marrow CR (mCR), partial remission (PR), stable disease (SD), partial or complete cytogenetic response, and hematologic improvement (HI). Additional efficacy measures of interest for the expansion AML cohort include CR with incomplete hematologic recovery (CRi), complete remission with partial hematologic recovery (CRh), morphologic leukemia-free state (MLFS), PR, SD, Cytogenetic CR (CRc), and molecular CR (CRm) per [Appendix 11](#).

The proportion of patients ever achieving each of the endpoints for the respective cohort will be estimated with two-sided 95% CI respectively.

CCI
[Redacted text block]

CCI [REDACTED]

[REDACTED]

[REDACTED]

[REDACTED]

[REDACTED]

CCI [REDACTED]

[REDACTED]

[REDACTED]

CCI [REDACTED]

[REDACTED]

CCI [REDACTED]

[REDACTED]

CCI

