Appendix 2. IWG Criteria: Response Criteria and Progression Definitions for Myelodysplasia***

Response Criteria (responses CR, PR, mCR must last at least 4 weeks)	Peripheral Blood				Bone Marrow Blasts (BMB) (%)	Other
	Hgb(g/dL)	Neutrophils (L)	Platelets (L)	Blasts (%)		
Complete Remission (CR)**	≥11	≥1 x 10 ⁹	≥100 x 10 ⁹	0	≤5	Normal maturation of all cell lines, note if has persistent dysplasia
Partial Remission (PR)**					Decreased by ≥50% but still >5%	All CR criteria if abnormal before treatment except BMB
Marrow CR (mCR)	If hematologic improvement (HI) response, note in addition to Marrow CR				≤5% & decreased by ≥50%	
Stable Disease*						Failure to achieve PR & no evidence of progression*
Failure						Death, or disease progression: worsening cytopenia, increase in % BM blasts, progression to a more advanced MDS FAB subtype
Relapse after (m)CR or PR					ICH	At least one of the following: Return to pre-treatment BMB % Decrement of ≥50% from maximum remission/response levels in granulocytes or platelets Reduction in Hgb ≥1.5g/dL or transfusion dependence

*SD must last >8 weeks but response is documented regardless of duration.

**Stability of the improved counts is sufficient to define CR or PR without the need to repeat a second BM.

***This criteria will be applied to MDS patients enrolled in the Safety Lead-In and Expansion components of the study and patients with AML with 20-30% blasts and multi-lineage dysplasia and CMML without proliferative disorder enrolled into the Safety Lead-In component of the study.

Additional Response Criteria for Myelodysplasia***

Cytogenetic Response Complete Partial	Disappearance of chromosomal abnormality with no appearance of new ones $\geq 50\%$ reduction of chromosomal abnormality
Disease Progression For patients with % blasts at screening: <5% bone marrow blasts 5-10% bone marrow blasts 11-20% bone marrow blasts 21-30% bone marrow blasts For all categories, any of:	$\geq 50\%$ increase to >5% bone marrow blasts $\geq 50\%$ increase to >10% bone marrow blasts $\geq 50\%$ increase to >20% bone marrow blasts $\geq 50\%$ increase to >30% bone marrow blasts At least 50% decrease from maximum remission/response in granulocytes or platelets Reduction in Hgb by ≥ 2 g/dL Transfusion dependence

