5. ANALYSIS SETS

5.1. Full Analysis Set (FAS)

The full analysis set will include all enrolled patients in the respective cohort (LIC, expansion MDS, and expansion AML cohort separately), who received at least one dose of any study treatment (PF-04449913 or azacitidine). This will be the primary analysis population for evaluating efficacy endpoints and patient characteristics.

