7.2. Efficacy Analysis

For primary and secondary efficacy analyses, no values will be imputed for missing data. Censoring for time-to-event endpoints are defined in [Section 6.1](#). In the assessment of response (at interim or final analysis), patients who are not known to have achieved response will be counted as non-responders.

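### MDS cytogenetic response is planned as a proportion of the whole FAS, which dilutes the rate with patients who have no baseline chromosomal abnormality and so cannot respond

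*SAP*

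**What the plan says.** SAP 8.2.2.2.2 (Other Efficacy Measures) ends its MDS list with "CR+PR, and Partial or Complete Cytogenetic Response, as well as the proportion of patients ever achieving HI". For AML it lists "proportion of patients achieving CR, CRh, CRi, CR/CRi, MLFS, PR, SD, CRc, , CRm, and CR+PR". Each measure gets an exact 95% interval, and the section closes with "The FAS will be used". SAP 5.1 puts into the FAS every enrolled patient in the cohort "who received at least one dose of any study treatment (PF-04449913 or azacitidine"), with no condition on baseline karyotype, marker or blood counts. SAP 7.2 adds that "patients who are not known to have achieved response will be counted as non-responders".

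Protocol 9.3.6 takes the same line: "The proportion of patients ever achieving each of the endpoints for the respective cohort will be estimated". For the lead-in cohort, SAP 8.2.2.1.2 limits HI to MDS patients but names no subset for cytogenetic response, and SAP 8.1 applies the FAS to all efficacy analyses.

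Protocol Appendix 2, repeated in SAP Appendix 2, defines a complete cytogenetic response as "Disappearance of chromosomal abnormality with no appearance of new ones". A partial response is a reduction of the abnormality by at least half. Protocol Table 3, footnote 17, requires karyotyping in all patients and states "Baseline genetics classification must be completed on a sample collected within 28 days prior to first dose".

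**The concern.** Cytogenetic response is a named secondary endpoint of the MDS cohort (Protocol 2.4). By its definition, a patient whose karyotype is normal at baseline has nothing to lose or reduce. Keeping such patients in the denominator makes the reported rate depend on two things at once: how often abnormalities clear, and how many enrolled patients had one. In a single-arm cohort of at most 30, the second can vary widely by chance and by case mix. The rate is then hard to read as a measure of activity, or to set beside another study, unless the reader also knows how many patients could have responded.

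**Working it through.** **1. The plan's own precision figure.** Protocol 9.1.2 gives a maximum exact 95% interval width of 0.374 for CR with 30 patients. The Clopper-Pearson interval is widest at 15/30: 0.313 to 0.687, width 0.3741. The figure reproduces. No precision is stated for cytogenetic response.

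**2. Can patients without an abnormality enter?** Yes. Protocol 4.1.2 asks for a WHO 2016 diagnosis and an IPSS-R score above 3. Under Appendix 10, marrow blasts above 10% give 3 points and hemoglobin of 8 to <10 gives 1. The total of 4 is Intermediate risk before any cytogenetic points are added. Appendix 12 accepts any karyotype for MDS-EB-1 and MDS-EB-2.

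**3. Formula.** Let n be the FAS size, m the number with a baseline abnormality, x the responders, and f = m/n. Then

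FAS rate = x/n = (m/n) × (x/m) = f × (rate among patients able to respond).

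The FAS rate cannot exceed f.

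**4. Illustration with n = 30 and x = 6.** Neither x nor f is in the documents; both are assumed.

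| Denominator | Assumed f | Rate | Exact 95% CI | Maximum CI width at this size |
|---|---|---|---|---|
| 30 (FAS) | – | 20.0% | 7.7% to 38.6% | 0.374 |
| 12 | 0.4 | 50.0% | 21.1% to 78.9% | 0.578 |
| 15 | 0.5 | 40.0% | 16.3% to 67.7% | 0.521 |
| 18 | 0.6 | 33.3% | 13.3% to 59.0% | 0.480 |

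Check: 0.4 × 50.0% = 0.5 × 40.0% = 0.6 × 33.3% = 20.0%.

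When most patients have an abnormality, the gap is small:

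- f = 0.8, 12 responders: 40.0% (22.7% to 59.4%) of 30 against 50.0% (29.1% to 70.9%) of 24.
- f = 0.9, 14 responders: 46.7% (28.3% to 65.7%) of 30 against 51.9% (31.9% to 71.3%) of 27.
- f = 1: no difference.

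**5. HI.** This depends on counts, not karyotype. Appendix 2 defines each lineage response only below a pretreatment limit: hemoglobin <11 g/dL, platelets <100 × 10⁹/L, neutrophils <1 × 10⁹/L. Appendix 12 sets the cytopenia limits for WHO-defined MDS at hemoglobin <10 g/dL, platelets <100 × 10⁹/L and neutrophils <1.8 × 10⁹/L. Meeting either of the first two automatically meets an HI limit. Those who may not qualify are mainly patients with isolated neutropenia of 1.0 to 1.8, the rare mild presentations noted in Appendix 12, and the CMML and MDS/MPN-unclassifiable patients whom Protocol 4.1.2 admits to this cohort.

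**6. CRc and CRm (AML).** Protocol 9.3.6 refers to Appendix 11 for the criteria. Neither Appendix 11 nor SAP Appendix 4 has a row for CRc or CRm, so who can respond cannot be determined.

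**The case against.** The strongest reply is that a proportion of all treated patients is a legitimate, prespecified descriptive rate. SAP 4.1 states no formal hypotheses, and none of these measures feeds the primary CR analysis or a stopping rule. That stands. A reader might infer that the FAS rate is a biased estimate or that its interval is wrong. The documents do not support this: the rate is correct for its own denominator and only diluted as a measure among patients able to respond.

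A reader might also infer that normal karyotype lowers HI and molecular response in the same way. It does not. SAP 6.1.2.1.2 derives HI from hematology and transfusion data, and nothing printed ties CRm to karyotype. For CRc and CRm, impossibility by definition cannot be shown while no definition is printed.

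The size is open to challenge too. At f = 0.4 or 0.5 in the illustration, the restricted estimate lies above the FAS upper limit of 38.6%, at f = 0.5 by only 1.4 points. At f = 0.6 it does not (33.3%), and every restricted interval overlaps the FAS interval.

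What the reply does not answer is that the MDS cytogenetic rate cannot be interpreted without its at-risk count, and no readable text calls for that count. One analysis set in SAP section 5 is blacked out, but 8.2.2.2.2 names the FAS explicitly. The plan restricts denominators elsewhere: SAP 8.2.2.2.3 and 8.2.2.2.4 use a named FAS subset, and 8.2.2.1.2 limits HI to MDS.

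**Conclusion.** The point holds for MDS partial or complete cytogenetic response, in the expansion cohort and in the completed lead-in of 12 patients. The FAS rate is lower than the rate among patients able to respond by the factor f whenever f is below 1. The direction follows from the definition; the size cannot be fixed from the documents. It ranges from a halving at an assumed f of 0.5 to about 5 percentage points in the f = 0.9 example. For HI the same logic applies only to patients with no lineage below its limit, and the effect is expected to be small. For CRc and CRm the finding is a missing definition, with the denominator to follow. The primary CR rate and the futility and safety rules are unaffected. This is a change that should be made to keep a secondary endpoint interpretable, not a flaw in the trial's main conclusion.

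**What to change.** In SAP 8.2.2.2.2 and 8.2.2.1.2:

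- **Cytogenetic response:** report it among FAS patients with a chromosomal abnormality at baseline, print the denominator, and keep the FAS proportion as a supporting line. State how a failed or missing baseline karyotype is classed.
- **HI:** use FAS patients in the MDS cohort with at least one lineage below its Appendix 2 pretreatment limit.
- **CRc and CRm:** add criteria to SAP Appendix 4 first, then apply the matching baseline-evaluable denominator.

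Baseline karyotype and blood counts are already collected, so the cost is mainly SAP wording and a few table lines. Protocol section 9 lets the SAP modify analyses other than that of the primary endpoint, so the denominators need no protocol amendment. The price is precision: the maximum interval width rises from 0.374 at 30 patients to 0.418 at 24, 0.480 at 18 and 0.521 at 15.

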8.2.2.2.3. DoCR

DoCR will be analyzed and displayed graphically for each expansion cohort separately using the Kaplan-Meier method. The median DoCR for each cohort and corresponding two-sided 95% CI will be provided.

The subset of patients in the FAS who have ever achieved CR on study will be used.

8.2.2.2.4. Time to Response (CR)

For patients in the expansion cohorts with an objective CR, TTR will be analyzed and displayed graphically for each cohort separately using the Kaplan-Meier method. The median TTR for each cohort and corresponding two-sided 95% CI will be provided.

The subset of patients in the FAS who have ever achieved CR on study will be used.

8.2.3. Analysis of Safety Data

Summaries and analyses of safety parameters will include all patients in the Safety Analysis Set for safety LIC and expansion cohorts.

Unless otherwise specified, the same definition applies to the endpoints in the safety LIC and the expansion component.

Adverse Events:

The focus of AE summaries will be on Treatment Emergent Adverse Events, those with initial onset or increasing in severity after the first dose of study medication. The number and percentage of patients who experienced any AE, serious AE (SAE), treatment related AE, and treatment related SAE will be summarized according to worst toxicity grades. The summaries will present AEs both on the entire study period and by cycle (Cycle 1 and Cycles beyond 1).

Laboratory Test Abnormalities:

The number and percentage of patients who experienced laboratory test abnormalities will be summarized according to worst toxicity grade observed for each lab assay. The analyses will summarize laboratory tests both on the entire study period and by cycle (Cycle 1 and all Cycles beyond 1). A shift summary of baseline grade by maximum post-baseline CTCAE grade will be presented.

For laboratory tests without CTCAE grade definitions, results will be categorized as normal, abnormal or not done.

8.2.3.1. Analysis of Primary Endpoint of Safety LIC

All patients who receive any study treatment will be included in the summaries and listings of safety data. Overall safety profile and tolerability will be characterized by type, frequency, severity, timing, and relationship to study therapy of adverse events and laboratory abnormalities.

Adverse events will be classified using the MedDRA classification system. The severity of the toxicities will be graded according to the NCI CTCAE version 4.03.

Safety analysis set for safety LIC will be used.

8.2.3.2. Analysis of Secondary Endpoint of Expansion Component

All patients who receive any study drug will be included in the summaries and listings of safety data. Overall safety profile and tolerability of PF-04449913 + azacitidine will be characterized by type, frequency, severity, timing, and relationship to study therapy of adverse events and laboratory abnormalities.

Adverse events will be classified using the MedDRA classification system. The severity of the toxicities will be graded according to the NCI CTCAE version 4.03.

The safety analysis set will be used for expansion MDS cohort and AML cohort, separately. The pooled analysis of safety data will utilize the combined LIC and expansion cohorts.

8.2.4. Pharmacokinetic Analyses

Analysis Set: PK Analysis set

PK Parameters:

For the safety LIC, standard plasma PK parameters including the observed maximum plasma concentration (C_{max}), time to maximum plasma concentration (T_{max}), and area under the plasma concentration versus time curve (AUC) for each drug (and metabolite if relevant), will be estimated using non-compartmental analysis. If data permit or if considered appropriate, plasma trough concentration (C_{trough}), average plasma concentration (C_{ave}) will be estimated.

For the expansion cohorts, the plasma trough concentration (C_{trough}) will be reported.

Presentation of pharmacokinetic data will include:

- Descriptive statistics (n, mean, SD, %CV, median, minimum, maximum) of plasma concentrations for PF-04449913 and azacitidine will be presented in tabular form by treatment cohort, dose level, cycle, day and nominal time.
- In the Phase 1b safety Lead-in, linear and semi-log plots of mean and median plasma concentrations by nominal time for PF-04449913 and azacitidine will be presented for PK sampling days by cycle, study day, and by treatment. Similar plots will be presented for each individual patient concentrations.
- Pharmacokinetic parameters (as treated and dose compliant groups) PF-04449913 and azacitidine will be listed and summarized by treatment cohort/dose level and study day using descriptive statistics (n, mean, SD, %CV, median, minimum, maximum, and geometric mean and its associated %CV). PK parameters with zero values will be excluded from the calculation of geometric means and its associated %CV. If an intra patient dose escalation or reduction occurs, data for that patient will only be included in descriptive statistics and summary plots up to the time of the dose change.
- Matchstick plots for C_{max} and AUC for PF-04449913 and azacitidine for the drug-drug interaction analysis dataset.

8.2.4.1. Evaluation of Drug-Drug Interaction Potential (Safety LIC)

The primary PK parameters, AUC and C_{max} , will be utilized to estimate the effect of co-administration of PF-04449913 and azacitidine on the PK of either PF-04449913 or azacitidine. The study is not powered to detect differences in PF-04449913 and azacitidine pharmacokinetics. ^{CCI}

If data permit and considered appropriate, the geometric mean ratios and its 95% confidence intervals for the PK parameters may be used for assessment of the extent of interaction for

PF-04449913+ azacitidine vs. PF-04449913 alone. A similar assessment may be conducted for azacitidine + PF-04449913 vs. azacitidine.

PF-04449913 AUC and C_{\max} when administered alone (Cycle 1/Day 15) will be compared to Cycle 1/Day 7 AUC and C_{\max} , when administered in combination with azacitidine. A similar assessment will be performed to determine the effect of PF-04449913 on azacitidine. The AUC and C_{\max} on Cycle 1 Day 1 when azacitidine is administered alone will be compared to Cycle 1/Day 7 AUC and C_{\max} when azacitidine is administered in combination with PF-04449913.

PK data from the lead-in portion of the PK analysis set will be used.

8.2.4.2. Population Pharmacokinetic Analysis or PK/PD Modeling

PK and PD data from this study may be analyzed using modeling approaches and may also be pooled with data from other studies to investigate any causal relationship between PF-04449913 exposure and biomarkers or significant safety endpoints. The results of these analyses, if performed, may be reported separately.

8.2.5. Electrocardiogram Analysis

The QT measurements corrected by heart rate (QTc) will be used for the data analysis and interpretation. QTcF (per Fridericia's correction) is planned to be the primary analysis method for the QTc endpoint. In addition a study-specific correction method (QTcS) and QTcB (per Bazett's correction) may also be evaluated for the QTc evaluable patients. The most appropriate correction method that eliminates any QT vs. RR relationship may be chosen after review of the data. Study conclusions will be based on the most appropriate correction method for the analysis.

8.2.5.1. Summary and Categorical Analysis of Electrocardiogram Findings

The analysis of ECG results will be based on patients with both baseline and on-treatment ECG data. All ECGs obtained during the study will be evaluated for safety. ECG collected prior to the first day of dosing (typically the pre-dose ECG prior to first dose of PF-04449913) will be considered the baseline ECG.

ECG measurements (an average of the triplicate measurements) will be used for the statistical analysis and all data presentations. Any data obtained from ECGs repeated for safety reasons after the nominal time-points will not be averaged along with the preceding triplicates. Interval measurements from repeated ECGs will be included in the outlier analysis as individual values obtained at unscheduled time points.

Data will be summarized and listed for QT, HR, RR, PR, QRS, QTcF and QTcB by treatment phase (safety LIC or expansion cohorts). Individual QTc (all evaluated corrections) intervals will be listed by time. The most appropriate correction factor will be selected and used for the following analyses of central tendency and outliers and used for the study conclusions.

Descriptive statistics (n, mean, median, standard deviation, minimum, and maximum) will be used to summarize the absolute QTc value and changes from baseline in QTc after treatment, and by treatment and time point. For each patient by treatment the maximum change from baseline will be calculated as well as the maximum post-baseline value across time-points. Outlier analysis of the QTc data will be conducted and summarized as follows:

- The number of patients with maximum change from baseline in QTc (<30, ≥ 30-<60, and ≥60 msec);
- The number of patients with maximum post-dose (post-baseline) QTc (≤450, >450-≤480, >480- ≤500, and >500 msec);
- PR changes from baseline ≥25% and absolute values >200 msec;
- QRS changes from baseline ≥25% and absolute values >110 msec;
- Number and percentage of individuals with abnormal ECG findings.

Shift tables will be provided for baseline versus worst on study QTc (one or more correction methods will be used) using Maximum CTCAE Grade. Tables of ECG abnormality at baseline (yes, no, not done: (n, %)) will also be provided. Patients experiencing clinically-relevant morphological ECG changes will be summarized (including frequency and percentage).

The QTc analysis set will be used.

